9.5 Outpatient Visits

9.5.1 After discharge from the hospital, patients will be seen weekly in the outpatient clinic for the first month. Patients will then be seen monthly for the next 6 months, regardless of which arm of the study they were randomized to. After six months of continuous follow-up patients will then be seen every 3 months for the next 3 years to monitor the course of their disease and obtain laboratory follow-up studies (see Appendix 1)

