14.3 Statistical Considerations-Correlative Laboratory Studies

The correlative biomarker outcomes described above will be descriptively summarized across and within treatment arms, and patterns in these changes in biomarkers and how they relate to treatment success, relapse, and TTP exacerbation will be explored graphically. For the study to determine the effects of corticosteroids and cyclosporine given individually on serial measurements of ADAMTS13 biomarker profiles and VWF multimeric patterns after their initial therapy and throughout longitudinal follow-up, we will evaluate these biomarkers in relation to the clinical outcomes of interest. For treatment success rates, we will evaluate baseline levels of these biomarkers to identify if there are any associations between these biomarkers and how these patients respond to treatment. These will first be explored graphically, also denoting those patients in the two different treatment arms. Logistic regression for whether or not the patient had a treatment success will be modeled with these baseline biomarkers as well as treatment arm.

In addition, we will compare the changes for each biomarker between the two groups. TTP exacerbations and relapses will be modeled separately. Both of these events are preceded by a period of clinical response where patients exhibit resolution of clinical signs and normal laboratory values. However, as stated above, there are important differences that warrant modeling TTP exacerbation and TTP relapses independently. First, the frequencies of specimen collection are different between the observation periods that lead to the exacerbation and relapses. The patients in the period of initial clinical response are monitored weekly, while the patients in the sustained clinical remission are followed quarterly. Secondly, the underlying pathophysiology for exacerbation and relapse are likely to be different. The disease exacerbation probably represents a continuation of an incompletely resolved disease while relapses of TTP most likely represent a de novo episode of TTP. As a result, the biomarkers that predict TTP exacerbation and relapse are likely to be different.

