To examine the potential of the 4 indices (ADAMTS13 activities, ADAMTS13 antigen levels, ADAMTS13 (IgG) autoantibody levels, and antibody inhibitor titers) to predict the recurrences of TTP, we will use the longitudinal data in two ways by separating indices obtained during the sustained clinical remission when they are measured every three months (quarterly) from those indices measured during the initial clinical response when patients are monitored weekly. The data for the relapse analysis will come from all quarterly samples collected from qualified study subjects during sustained remission. The outcome of interest will be whether or not the

individual experiences a relapse of TTP during the three months following the date the measurements are taken. We anticipate obtaining a total of >400 observations that will correspond to approximately >16 events of relapse and other quarterly measurements ($n \sim 400$) without relapses. For analysis of exacerbation in initial clinical remission, the outcome of interest will be whether or not the individual experiences an event of exacerbation in the week following the measurement. The weekly samples in initial clinical remission from the same group of study subjects will be analyzed. We anticipate a total of about 200 weekly data points, corresponding to about >16 measurements with events of exacerbation and 200 measurements without events in the week following measurement. We will use the logistic regression model to analyze all 4 indices independently as well as to evaluate their interacting effects.

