Since each individual has several observations, possibly with and without relapse or exacerbation, this would induce a special correlation structure. For this reason, we will introduce random effects into the model (53-55). The covariates corresponding to gender, age, race, and treatment modalities (e.g. CSA vs. corticosteroids) will also be evaluated in the model. Additionally, various variance-covariance structures will be investigated. The Generalized Estimation Equation will also be used if necessary if our specific covariance structures lead to un-interpretable results. Since the number of predictor variables is relatively small, a standard traditional model selection procedure will likely be feasible to study the reach of the predictors as well as their interacting effects. Various model selection criteria such as Ra2, Mallows Cp, AIC, and BIC will be used to evaluate the putative models. In the case where samples are not available on all subjects at consistent timepoints, we will utilize the more flexible growth curve modeling approach to identify changes over time in the biomarker on the incidence and time to relapse as well as TTP exacerbation.

VWF multimer patterns form a relatively complex dataset. We will dissect VWF patterns into several parameters that will all give rise to a continuous measurement. This will be the density of VWF multimers in bands 1 through 15 and the area above band 15. All data will be normalized by the reference plasma included in each gel. For investigating the relationship between ULVWF (area above band 15) and relapse in the quarter immediately following, a logistic regression analysis as described will be performed. Specifically, the response variable will be 1 or 0, depending on whether relapse has occurred or not. The explanatory variable will be the ULVWF value at the beginning of the quarter-interval, with a random effect also included to account for correlations among the different response variable observations over time in a given patient. The effects of other covariates will be included in the model and adjusted for as necessary.

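### The relapse-prediction models in Section 14.3 take quarterly samples only, so the scheduled monthly samples and relapses before the first quarterly sample enter no specified prediction model

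*Combined protocol and SAP*

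**What the plan says.** Section 14.3 splits the longitudinal biomarker data into two sets. Its premise is: "The patients in the period of initial clinical response are monitored weekly, while the patients in the sustained clinical remission are followed quarterly". Weekly samples go to a logistic model for exacerbation in the following week. For relapse within the next three months, the rule is: "The data for the relapse analysis will come from all quarterly samples collected from qualified study subjects during sustained remission". The model for ultra-large VWF (ULVWF) follows the same grid: "The explanatory variable will be the ULVWF value at the beginning of the quarter-interval". The plan expects more than 400 quarterly observations with more than about 16 relapses, and about 200 weekly points.

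The visit schedule has a third phase between these two. After the weekly first month, Section 9.5.1 says: "Patients will then be seen monthly for the next 6 months, regardless of which arm of the study they were randomized to". It continues: "After six months of continuous follow-up patients will then be seen every 3 months for the next 3 years". Section 9.4.3 takes the ADAMTS13 and VWF samples at every one of these visits. Appendix 1 places the monthly samples at weeks 8, 12, 16, 20, 24 and 28, and the quarterly ones from week 40 to week 160. Section 8.4.2 classes any recurrence later than 30 days after PE ends as a relapse.

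Other parts of Section 14.3 also bear on this. There is a contingency: "In the case where samples are not available on all subjects at consistent timepoints, we will utilize the more flexible growth curve modeling approach". On covariates: "The covariates corresponding to gender, age, race, and treatment modalities (e.g. CSA vs. corticosteroids) will also be evaluated in the model". On model choice: "Various model selection criteria such as Ra2, Mallows Cp, AIC, and BIC will be used to evaluate the putative models".

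**The concern.** The premise in Section 14.3 that sustained remission is sampled quarterly does not match the schedule. A patient who relapses at month 3 or 4 has a study relapse and has given several biomarker samples beforehand, yet no specified prediction model receives those samples or that event. Such a patient stays in follow-up under Section 8.5.2, so later quarterly samples might enter the model while the early relapse does not.

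What is at stake is the secondary objective in Section 1.2 of finding laboratory markers prognostic for relapse. The omitted stretch is not a random part of follow-up. Cyclosporine (CSA) runs for six months (Section 7.3.2), and Appendix 1 lists no CSA level at week 28. The relapse models would therefore omit nearly all on-CSA time after the exacerbation window. Prednisone ends after a four-week taper that starts on day 31 after PE (Section 7.2.2), so the treatment covariate in these models would compare the arms when both are essentially off study drug. Section 3.3 reports a gradual decline after CSA is stopped, so a marker's relation to relapse on drug may differ from its relation off drug.

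A smaller point concerns model selection. Ra2 (adjusted R-squared) and Mallows Cp are least-squares criteria and do not suit random-effects logistic models.

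**Working it through.** **The plan's own figure.** The plan gives no derivation for the >400 observations or the >16 relapses, so neither can be reproduced uniquely. A plausibility check is possible:
- Patients in remission at day 30, taking the planned success rates of 50% and 80% in Section 14.1 as a stand-in: 36 × 0.5 + 36 × 0.8 = 46.8.
- Quarterly intervals ending at a scheduled visit: 11 if week 28 opens the first (28 to 160), 10 if week 40 does (40 to 160).
- Observations before dropout: 46.8 × 11 = 515, or 46.8 × 10 = 468. Both are compatible with >400.

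**Samples left out.** Appendix 1 has 6 monthly samples and 11 quarterly samples after week 4, 17 in all. Week 160 has no later visit, so 16 samples can be followed to a next visit.
- Week 28 opens a quarter: weeks 8 to 24 unused, 5/16 = 31%.
- Week 40 opens a quarter: weeks 8 to 28 unused, 6/16 = 38%.

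**Follow-up left out.** Week 4 is taken as about day 30 after PE, which assumes discharge close to the last exchange. Weeks 4 to 160 are 156 weeks.
- To week 28: 24/156 = 15%.
- To week 40: 36/156 = 23%.

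These shares need no event rate.

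**Relapses that could be added.** The plan's figures imply a rate of 16/(16 + 400) = 16/416 = 3.85% per quarter. With k quarters omitted (2 to week 28, 3 to week 40), the expected number is 46.8 × [1 − (1 − r)^k].

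| Rate per quarter, r | k = 2 | k = 3 |
|---|---|---|
| 2% (assumed) | 1.9 | 2.8 |
| 3.85% (implied) | 3.5 | 5.2 |
| 6% (assumed) | 5.4 | 7.9 |

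For example, at 3.85% and k = 2: 46.8 × (1 − 0.9615²) = 46.8 × 0.0754 = 3.5. The table assumes one constant rate on and off CSA and no dropout.

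**Effect on precision.** If standard errors scale with one over the square root of the number of events, moving from 16 to 19.5 events gives √(16/19.5) = 0.906, about 9% smaller. Moving from 16 to 21.2 gives √(16/21.2) = 0.869, about 13% smaller.

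**The case against.** Much of the case on the other side stands.

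- **The early relapses are not lost to the trial.** They count in the relapse rate and the Kaplan-Meier analysis (Section 14.2). Section 14.3 also compares biomarker changes between arms and summarises them graphically, without restricting this to quarterly samples. The treatment term in the relapse models is one covariate among several, not the trial's comparison of the arms.
- **The 16 expected relapses are not reduced.** A reader might infer that 3.5 to 5.2 of them disappear. The plan ties that figure to the quarterly observations, so early relapses would be additional events.
- **The pilot does not show clustering.** A reader might infer from Section 3.2 that relapses concentrate in the omitted months, because two upfront-CSA patients recurred at 3 and 4 months. That section reports recurrences on CSA and does not say whether anyone relapsed after stopping. It shows only that relapses can occur in this period.
- **The extent of the gap is open.** The terms sustained remission and qualified study subjects are not defined. Weeks 4, 16, 28 and 40 are 12 weeks apart, so week 16 could be read as a quarter start. The gap would then be 12/156 = 8% of the weeks and, at the implied rate, 46.8 × 0.0385 = 1.8 relapses. Against this reading, Section 9.5.1 starts three-monthly visits only after six months.
- **The growth-curve approach might use these samples.** Its condition could well be met, since clinic visits are timed from discharge. It is still only a contingency, and it does not mention the monthly phase.
- **Pooling brings its own problem.** For most of the monthly phase one arm is on drug and the other is off. A single time-constant arm term would mix the two states, so study-drug status has to be in the model.

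A quarterly-only model with one fixed horizon is defensible as a deliberate choice. Section 14.3 does not present it as one: it describes sustained remission as if the monthly phase did not exist.

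**Conclusion.** The point holds as a minor-to-moderate one on a secondary objective. As written, Section 14.3 assigns the monthly samples, and relapses from day 31 until the first quarterly sample, to no specified prediction model. That is 31% or 38% of the usable later samples and 15% or 23% of the scheduled weeks, depending on whether week 28 or week 40 opens the first quarter. These shares rest on the Appendix 1 calendar; the share of weeks also takes week 4 as about day 30 after PE.

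The number of relapses that could be added is less certain: about 3.5 to 5.2 at the plan's implied rate, and 1.9 to 7.9 across assumed rates of 2% to 6% per quarter. The implied rate comes from two figures without derivation and is assumed equal on and off CSA. The gain in precision is modest. The stronger reason to act is that the omitted period holds nearly all on-CSA time at risk of relapse. The documents do not support a conclusion that the primary endpoint, the relapse rate or the comparison of relapse between arms is affected.

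**What to change.** In Section 14.3:

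1. Correct the statement that sustained remission is followed quarterly, and say whether week 28 opens the first quarter.
2. Build the relapse datasets (four indices and ULVWF) from all monthly and quarterly samples of qualified study subjects taken beyond day 30 after the last PE. Let the last weekly sample open the first interval. Define qualified study subjects.
3. Analyse steroid-arm patients who switch to CSA after an exacerbation separately, as Section 8.5.1 already requires, and state how samples taken after a relapse are handled.
4. Keep the random effect and choose one outcome definition. Either use relapse before the next scheduled sample, in a complementary log-log model with log interval length as offset, or keep the three-month horizon for every sample and allow for overlapping windows.
5. Include on/off study drug as a time-varying covariate, and report the quarterly-only model as a sensitivity analysis.
6. For the likelihood-based logistic models, use the AIC and BIC already listed and drop Ra2 and Mallows Cp.

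The cost is SAP wording and slightly more analysis work. The samples are already scheduled, so there are no new visits or draws. The first outcome definition assumes a constant hazard within each interval and gives up the fixed three-month horizon; the second brings overlapping outcome windows.

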3.3 Combined Analysis: ADAMTS13 Activity, Antigen and Inhibitor After Concurrent CSA and PE

Patients on both cohort studies (exacerbation/refractory study and upfront study) of CSA and PE were followed serially to study the effect of CSA on ADAMTS13 activity, antigen, and inhibitor concentration and correlated with clinical outcome data. Complete ADAMTS13 and inhibitor data obtained serially for all CSA and PE treated patients during and after the 6 month period of CSA therapy is shown graphically in Figure 1. Although not randomized, these data suggest that cyclosporine improved ADAMTS13 activity via the suppression of the inhibitory IgG antibody. Although it could be argued that the improvement in ADAMTS13 activity could have resulted from PE therapy, the significant delay before the improvement in the ADAMTS13 activity argue that the CSA resulted in the suppression of the inhibitory antibody and the improvement in ADAMTS13 activity. Furthermore, the gradual decline seen after the discontinuation of CSA also support the hypothesis that it was the CSA and not the delayed effect of PE that resulted in the steady improvement in ADAMTS13 activity seen in this cohort of patients.

[figure not shown]

Figure 1. Serial determinations of the mean ADAMTS13% activity and inhibitor concentration throughout clinical follow-up both during and after therapy with cyclosporine. The arrow at the top of each graphs represent the duration of therapy with cyclosporine.

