8.4 Exacerbation/Relapse Determination

8.4.1 Criteria to determine recurrences of disease and the need for re-initiation of therapy with plasma exchange will be the same as those to diagnose TTP (section 5.2.1). Patients requiring the reinstitution of plasma-based therapy (plasma exchange or infusion) within the first 30 days after discontinuing PE will be considered to have an “exacerbation” of their TTP.

8.4.2 Patients with a recurrence of TTP at a time point greater than 30 days from the end of plasma exchange therapy will be considered to have a "relapse" for the purposes of this study.

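### The weekly exacerbation model in Section 14.3 has no term for time since last plasma exchange, and its week-4 samples are near-automatic non-events

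*Combined protocol and SAP*

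**What the plan says.** Section 14.3 makes each weekly sample one record. The outcome is "whether or not the individual experiences an event of exacerbation in the week following the measurement". On which records enter, it says "The weekly samples in initial clinical remission from the same group of study subjects will be analyzed", and it expects "about >16 measurements with events of exacerbation and 200 measurements without events in the week following measurement". On the model it says "We will use the logistic regression model to analyze all 4 indices independently as well as to evaluate their interacting effects". Random effects handle repeated records per patient, with GEE as a fallback. On adjustment: "The covariates corresponding to gender, age, race, and treatment modalities (e.g. CSA vs. corticosteroids) will also be evaluated in the model".

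No week, visit or days-since-PE term is named. Time enters only through a growth-curve alternative, reserved for the case where subjects are not sampled at consistent times.

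The outcome and the sampling run on different clocks. Under Section 8.4, patients who go back onto plasma-based treatment "within the first 30 days after discontinuing PE will be considered to have" an exacerbation; a later recurrence is a relapse. Sections 9.4.1 and 9.5.1 and the notes to Appendix 1 count weekly visits from hospital discharge. Appendix 1 shows inpatient treatment continuing until PE has been tapered and stopped.

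**The concern.** Section 1.2 lists finding markers prognostic for exacerbation as a secondary objective. In pooled patient-week data, calendar position can stand in for prognosis. If the chance of an event falls over the four weeks, and a marker's mean moves over the same weeks for unrelated reasons, a model without time credits the marker with the trend.

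Part of the fall in risk is built into the definitions, because the last weekly records have little or no time left in which an exacerbation can be counted. At stake is whether an ADAMTS13 index is reported as prognostic when it partly tracks days since the last exchange.

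**Working it through.** **1. The plan's record count.** The pilot remission rates (10/12 on steroids, Section 2.6; 11/12 on CSA, Section 3.2), applied to 36 patients per arm, give 36 × 10/12 + 36 × 11/12 = 30 + 33 = 63 responders. With four weekly samples each, follow-up ending at exacerbation and 16-20 events, this gives about 204-227 records. That brackets the plan's 200 + 16 = 216. Three samples each would give at most 63 × 3 = 189, so the plan's count suggests that week-4 records are included. This inference rests on the pilot rates: if all 72 patients responded, 72 × 3 = 216 before censoring.

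**2. Days at risk.** Let discharge fall L days after the last PE. Appendix 1 implies L ≥ 0. Taking the week-w visit as 7w days after discharge, the sample is on day 7w + L, and

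days at risk in the outcome week = min(7, max(0, 30 − (7w + L))).

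For w = 4 this is max(0, 2 − L): 2 days if L = 0, 1 day if L = 1, none if L ≥ 2. For w = 3 it is min(7, 9 − L) for L up to 9, a full week while L ≤ 2.

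**3. Why the named terms do not absorb this.** The planned model is logit P(event) = α + β·marker + γ·(gender, age, race, treatment) + patient effect. Every term except the marker is constant within a patient. A time trend common to all patients can therefore load on β.

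**4. Simulation of a marker with no prognostic value.** The documents give neither weekly risk nor weekly marker drift, so both are assumed. Plain logistic regression, 60 responders, 18 events, drift shared by all patients, within-patient correlation 0.5, 1000 runs, no time term. Entries are false positives at nominal 5%, with median odds ratio (OR) per SD:

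| Week-1/week-4 risk ratio | drift 0 | 0.25 SD/week | 0.5 SD/week | 1.0 SD/week |
|---|---|---|---|---|
| 1 (flat) | 3.9% (1.00) | 4.6% (1.00) | 4.9% (1.00) | 4.1% (1.00) |
| 2 | 5.4% (1.01) | 5.8% (0.94) | 8.6% (0.88) | 10.9% (0.81) |
| 4 | 4.4% (1.00) | 8.0% (0.87) | 17.2% (0.76) | 32.0% (0.67) |
| 8 | 5.9% (0.99) | 13.5% (0.83) | 27.6% (0.70) | 55.9% (0.57) |

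GEE (63 responders, 16 events, 400 runs) gives 10-38% at ratio 4 and 13-58% at ratio 8. Bias needs both ingredients: with no drift, or with flat risk, the OR stays at about 1.

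A separate check at 0.5 SD/week, with shared drift and truncated or declining risk, gave about 9-27%.

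**5. The random-intercept model the plan puts first.** Maximum likelihood, 63 responders, about 16 events, 200 runs, shared drift 0.25-0.75 SD/week:

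| Weekly risk | plain logistic | GEE | random intercept |
|---|---|---|---|
| 14/9/5/1% | 9-41% | 11-48% | 5-7% (OR 0.81-0.89) |
| week-4 risk zero | 7-15% | 10-26% | 6% (OR 0.87-0.94) |

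Under 14/9/5/1% the fitted patient SD has a median of 3.3-3.9 logits where the true value is 0. The trend is partly absorbed as false patient heterogeneity.

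**6. Drift on CSA only, treatment in the model.** At 0.5 SD/week, false positives are about 3-9% with OR 0.92-0.95. A second run (62 patients, 15-16 events, 80% of events assumed on steroids, 500 runs) gave 4-9% with OR 0.93-0.97 under week-4 truncation, and 5-8% with OR 0.87-0.95 under 14/9/5/1% risk.

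**7. With a linear week term.** In the step 4 scenarios, false positives are 3.7-5.5% (logistic; OR 0.97-1.01) and 5.8-8.0% (GEE, a small-sample excess). In the 14/9/5/1% scenario of step 5 they are 5.5-6.5% for all three methods, with OR 0.98 for logistic and random intercept.

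**The case against.** The strongest objection is to the drift. Section 3.3 describes "the significant delay before the improvement in the ADAMTS13 activity" on CSA, seen over a course of months. A delay is not evidence of a rise across the first four weekly samples. For steroids the documents report the opposite of recovery: Section 2.6 found no significant improvement in activity at remission, and Section 2.5 describes two patients without lasting improvement. A drift shared by both arms is therefore an assumption. When it is confined to CSA and treatment is in the model, most of the inflation disappears. This stands, and it limits the size of the point.

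The random-intercept model comes first in the plan and shows little false-positive inflation. That also stands, but its OR is still biased. The plan's fallback, if the covariance structures give results that cannot be interpreted, is GEE, which shows the largest inflation in step 5. A spuriously large patient variance could plausibly trigger that switch.

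The growth-curve clause could be read as covering visits tied to discharge, and the covariate list is not said to be exhaustive. But the clause is conditional and concerns change in the biomarker; neither it nor the list puts time since PE into this model. One could also argue that samples after day 30 no longer belong to the initial remission, but Section 14.3 sets no such cut-off.

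Finally, a marker-only model is a legitimate prognostic question. That is a reason to show both models. It does not justify records with no days at risk.

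**Conclusion.** The point holds as a cheap improvement to a secondary correlative analysis. The omission of time and the truncated week-4 outcome follow from the plan's own definitions, given L ≥ 0 and visits at weekly steps from discharge. Bias in the odds ratio then requires a marker that drifts over the same weeks.

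Its size cannot be fixed from the documents. At 0.5 SD/week, false positives are roughly 9-27% with shared drift and non-flat risk (plain logistic or GEE), and about 3-9% with OR 0.92-0.95 if drift is on CSA only and treatment is modelled. Flat risk gives no bias.

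A reader might infer that the planned analysis will declare ADAMTS13 indices prognostic falsely, or that the largest simulated rates describe this trial. The documents do not support that: those rates need a steep fall in risk and a strong drift common to both arms, and the plan reports neither. A reader might also extend the point to the quarterly relapse models, but no calculation here bears on them.

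**What to change.** In Section 14.3, for the weekly exacerbation models only:

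- Pre-specify one linear term for days since last PE. Week indicators would cost up to three degrees of freedom, too many for about 16 events.
- Limit records to outcome days within 30 days of the last PE. Drop records with no at-risk days. For partial weeks, either exclude the record or use a complementary log-log link with a log(days at risk) offset; that offset does not suit a logit link.
- Show the model without the time term alongside.

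The change is to wording and uses PE and sample dates the trial should already hold. It costs about one degree of freedom and slightly wider intervals, and the marker effect is then read as conditional on time since PE. Excluding partial weeks would also lose any event falling in them.
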